4.2.6 Exploratory biomarkers

The exploratory biomarker variables are:

- Protein and metabolites changes that may be measured to understand the cause, progression, and appropriate treatment of CIDP
- Exploratory biomarkers such as, but not limited to, [REDACTED]
[REDACTED]
- Absolute change from Baseline relating to mechanism of action, disease activity, treatment response, and clinical outcome at each scheduled assessment during the Treatment and Observation Periods

5 STUDY DESIGN

5.1 Study description

This is a Phase 2A, multicenter, single-arm, OLE study to evaluate the safety, tolerability, and efficacy of rozanolixizumab during long-term treatment of study participants with CIDP from a previous study with rozanolixizumab.

Access to CIDP04 for study participants coming from CIDP01: Study participants from CIDP01 who have completed the Treatment Period (ie, all visits up to Visit 17) without a relapse of CIDP will be offered the opportunity to be directly enrolled into this OLE study. Study participants will enter CIDP04 on the same day as the last study visit in CIDP01: Visit 17. Study participants from CIDP01 who have experienced a relapse of CIDP (during either the Treatment Period or the Observation Period), have been successfully rescued and stabilized with SOC medication and have consented to enter this OLE study, may be assessed for eligibility. The study participants who relapsed during the Treatment Period of CIDP01 will be offered entry into CIDP04 only once CIDP01 study results are available, after the blind has been broken at the end of the study, and it is confirmed they received placebo in CIDP01.

In case the study participants have a gap period between the end of the parent study and the start of this OLE study (ie, last visit in the parent study does not take place on the same day as entry of study CIDP04), a Screening Period of 2 to 5 weeks will be applicable to confirm that the study participant still meets the eligibility criteria for entry in the OLE study and allow for a smooth transition between the treatment used by the study participants during the gap period and the initiation of rozanolixizumab. The CIDP04 study includes a first 24-week Treatment Period (Part 1) followed by a second Treatment Period (Part 2) of up to 52 weeks (or until an Access Program or equivalent is in place, whichever comes first). Entry to the Treatment Period (Part 2) will be contingent to a favorable individual benefit-risk after careful individual assessment has been performed for each study participant completing Treatment Period (Part 1). An 8-week Observation Period will be followed in case of premature termination or after completion of the Treatment Periods (either at end of Part 1 for study participants not continuing in Part 2 or at end

of Part 2). The Observation Period will not be performed in the event of a study participant continuing treatment with rozanolixizumab after the end of the study (ie, in case of an Access Program), in which case only the PEOT (Visit 26) Visit will be performed.

During the Treatment Periods (Part 1 and Part 2), study participants will have weekly visits (either on site or at home) during which they will be dosed with an sc infusion of rozanolixizumab up to [REDACTED]. The initial dose in the study will be based on the dose the study participant has received at the completion of the parent study (eg, CIDP01). For study participants who were known to be on placebo in the parent study, a starting dose of [REDACTED] will be used. The maximum dose will be [REDACTED]. See Section 7.2 for details on treatment to be administered.

During the first 4 weeks of the Treatment Period (Part 1), all visits will be on site. During Weeks 5 to 8, home visits and on-site visits will be alternating (Weeks 5 and 7 will be on site; Weeks 6 and 8 will be at home). Starting at Week 9 and through the end of the Treatment Period (Week 24 and if applicable, Week 76), study participants will have 1 visit on site followed by 3 visits at home for every 4-week period.

After the completion of the Treatment Period(s) (starting at Week 25 for study participants only completing Part 1 or from Week 77 for study participants completing both Part 1 and Part 2 or at any early timepoint in case of PEOT), study participants will enter the 8-week Observation Period where no IMP will be administered. During the Observation Period, study participants will have on-site visits at the entry and exit of the Observation Period (Weeks 25/77, and 32/84, and home visits at Weeks 27/79 and 29/81). Study participants can return to their SOC during the Observation Period. In case the study participant enters an Access Program, no Observation Period will be performed with the exception of the PEOT (Visit 26) Visit which will be immediately completed.

At the discretion of the investigator and/or study participant, home visits can be changed to site visits (eg, for safety reasons). In case an on-site visit cannot be performed, the next visit will be performed at site instead of at home, and all safety assessments that should have been completed at the missed visits will be performed.

The assessments to be completed during each visit are presented in Table 5-1.

5.1.1 Study duration per study participant

The total duration of the study for an individual study participant will be up to 89; this includes a 2- to 5-week Screening Period, a 24-week Treatment Period (Part 1), an optional maximum 52-week Treatment Period (Part 2), or until an Access Program or equivalent is in place whichever comes first, and an 8-week Observation Period in case the participant does not enter in an Access Program (or equivalent).

The end of the study is defined as the date of the last visit of the last study participant in the study.

5.1.2 Planned number of study participants and sites

A total of [REDACTED] study participants participating in the parent study CIDP01 may be enrolled in this OLE study; enrollment is planned at approximately 24 sites.

Depending on the further development of the UCB CIDP program, there may also be an opportunity for additional, future CIDP patients to enroll into CIDP04 from other parent studies at a later time point.

5.1.3 Anticipated regions and countries

Anticipated regions are Europe, United States of America, and Canada, with possible extension to other regions and countries.

5.2 Schedule of study assessments

The schedule of study assessments are provided in [Table 5-1](#).

PUBLIC COPY
This document cannot be used to support any marketing application and any extensions or variations thereof.

Table 5-1: Schedule of study assessments

Assessments	Visit	1 Scr ^b	24-Week Treatment Period (Part 1)												52-Week Additional Treatment Period (Part 2 - Optional) ^a		8-Week Observation Period (Optional)			
			2 BL	3	4	5	6	7	8	9	10 14 18 22	11 15 19 23	12 16 20 24	13 17 21 25	Additional Visits numbered sequentially	26 PEOT	27	28	29 FV	
	Week	-5 to -2	1	2	3	4	5	6	7	8	9	10 13 17 21	11 14 18 22	12 15 19 23	Every 4 weeks	Weekly in between site visits	25 or 77	27 or 79	29 or 81	32 or 84
Visit type ^c	S	S	S	S	S	S	H ^d	S	H ^d	S	H ^d	H ^d	H ^d	H ^d	S	H ^d	H ^d	H ^d	S	
Written informed consent ^e	X	X																		
Demographic data ^e	X	X																		
Verification of inclusion and exclusion criteria ^e	X	X																		
Withdrawal criteria			X	X	X	X	X	X	X	X	X	X	X	X	X	X	X	X	X	
Medical history update ^e	X	X																		
Prior and concomitant medication	X	X ^f	X	X	X	X	X	X	X	X	X	X	X	X	X	X	X	X	X	
Concomitant medical procedures	X	X ^f	X	X	X	X	X	X	X	X	X	X	X	X	X	X	X	X	X	
Vital signs ^g	X	X	X	X	X	X	X	X	X	X	X	X	X	X	X	X	X	X	X	

Table 5-1: Schedule of study assessments

Assessments	Visit	1 Scr ^b	24-Week Treatment Period (Part 1)												52-Week Additional Treatment Period (Part 2 - Optional) ^a		8-Week Observation Period (Optional)			
			2 BL	3	4	5	6	7	8	9	10 14 18 22	11 15 19 23	12 16 20 24	13 17 21 25	Additional Visits numbered sequentially	26 PEOT	27	28	29 FV	
	Week	-5 to -2	1	2	3	4	5	6	7	8	9	10 13 17 21	11 14 18 22	12 15 19 23	Every 4 weeks	Weekly in between site visits	25 or 77	27 or 79	29 or 81	32 or 84
Body weight		X	X ^f												X ^h		X			X
Recording of AEs		X	X ^f	X	X	X	X	X	X	X	X	X	X	X	X	X	X	X	X	X
Query for suicidality ⁱ		X	X ^f	X	X	X	X	X	X	X	X	X	X	X	X	X	X	X	X	X
Fatigue scale			X ^f			X				X					X ^j		X			X
CIDP PRO Instrument			X ^f			X				X					X ^j		X			X
PGIS			X ^f			X				X					X ^j		X			X
PGIC			X ^{fk}			X				X					X ^j		X			X
Full physical examination		X	X ^f																	X
Brief physical examination				X	X	X	X		X		X				X		X			

Table 5-1: Schedule of study assessments

Assessments	Visit	1 Scr ^b	24-Week Treatment Period (Part 1)												52-Week Additional Treatment Period (Part 2 - Optional) ^a		8-Week Observation Period (Optional)			
			2 BL	3	4	5	6	7	8	9	10 14 18 22	11 15 19 23	12 16 20 24	13 17 21 25	Additional Visits numbered sequentially	26 PEOT	27	28	29 FV	
	Week	-5 to -2	1	2	3	4	5	6	7	8	9	10 13 17 21	11 14 18 22	12 15 19 23	Every 4 weeks	Weekly in between site visits	25 or 77	27 or 79	29 or 81	32 or 84
Full neurological examination ¹		X	X ^f																	X
Brief neurological examination				X	X	X	X		X		X		X			X		X		
12-lead ECG		X	X ^f	X	X	X			X		X		X		X ^m		X			X
Labs (hematology, chemistry, urinalysis)		X	X ^f	X	X	X			X		X		X		X		X			X
Serology for HIV, hepatitis B, and hepatitis C ⁿ		X																		
Serum/urine pregnancy test ^o	X	X ^f	X	X	X	X	X	X	X	X	X	X	X	X		X	X	X	X	
IGRA tuberculosis test ^p	X	X ^f																		X

Table 5-1: Schedule of study assessments

Assessments	Visit	1 Scr ^b	24-Week Treatment Period (Part 1)												52-Week Additional Treatment Period (Part 2 - Optional) ^a		8-Week Observation Period (Optional)			
			2 BL	3	4	5	6	7	8	9	10 14 18 22	11 15 19 23	12 16 20 24	13 17 21 25	Additional Visits numbered sequentially	26 PEOT	27	28	29 FV	
	Week	-5 to -2	1	2	3	4	5	6	7	8	9	10 13 17 21	11 14 18 22	12 15 19 23	Every 4 weeks	Weekly in between site visits	25 or 77	27 or 79	29 or 81	32 or 84
Tuberculosis Signs and Symptoms Questionnaire		X													X ^q	X ^q				X
Contact IRT		X	X	X	X	X	X	X	X	X	X	X	X	X	X	X	X			X
Administration of IMP			X	X	X	X	X	X	X	X	X	X	X	X	X ^r	X ^r				
Blood sampling for PK of rozanolixizumab ^s		X ^f		X				X		X ^t					X ^m		X			
ADA (Anti-rozanolixizumab antibodies)		X ^f		X				X		X ^t					X ^m		X			X
Serum complement (C3, C4) and plasma complement (C3a, C5a) ^u		X	X					X		X					X					

Table 5-1: Schedule of study assessments

Assessments	Visit	1 Scr ^b	24-Week Treatment Period (Part 1)												52-Week Additional Treatment Period (Part 2 - Optional) ^a		8-Week Observation Period (Optional)			
			2 BL	3	4	5	6	7	8	9	10 14 18 22	11 15 19 23	12 16 20 24	13 17 21 25	Additional Visits numbered sequentially	26 PEOT	27	28	29 FV	
	Week	-5 to -2	1	2	3	4	5	6	7	8	9	10 13 17 21	11 14 18 22	12 15 19 23	Every 4 weeks	Weekly in bet- ween site visits	25 or 77	27 or 79	29 or 81	32 or 84
Serum cytokines ^u			X	X					X		X					X				
Vaccination-specific antibody titers (tetanus and influenza Type A)		X							X		X ^v				X ^m		X			
Immunoglobulins (total IgG and IgG subclasses)	X	X ^f	X	X	X	X	X ^w	X	X ^w	X	X ^w	X ^w	X ^w	X ^w	X	X ^w	X			X
NF-L		X ^f							X						X ^x		X ^y			
IgA, IgM, IgE		X ^f	X	X	X	X		X		X				X ^m		X			X	
CIDP-specific auto-antibodies		X ^f				X				X				X ^x		X ^y			X ^x	

Table 5-1: Schedule of study assessments

Assessments	Visit	1 Scr ^b	24-Week Treatment Period (Part 1)												52-Week Additional Treatment Period (Part 2 - Optional) ^a		8-Week Observation Period (Optional)			
			2 BL	3	4	5	6	7	8	9	10 14 18 22	11 15 19 23	12 16 20 24	13 17 21 25	Additional Visits numbered sequentially	26 PEOT	27	28	29 FV	
	Week	-5 to -2	1	2	3	4	5	6	7	8	9	10 13 17 21	11 14 18 22	12 15 19 23	Every 4 weeks	Weekly in between site visits	25 or 77	27 or 79	29 or 81	32 or 84
	Visit type ^c	S	S	S	S	S	S	H ^d	S	H ^d	S	H ^d	H ^d	H ^d	S	H ^d	S	H ^d	H ^d	S
Blood sampling for exploratory biomarker analysis ^z			X	X					X		X									
iRODS assessment ^{aa}		X	X ^f	X	X	X	X		X		X				X		X			X
INCAT assessment		X	X ^f	X	X	X	X		X		X				X		X			X
Assessment of grip strength by site personnel		X	X ^f	X	X	X	X		X		X				X		X			X
RT-MRC assessment		X	X ^f	X	X	X	X		X		X				X ^x		X ^y			X ^x

Table 5-1: Schedule of study assessments

Assessments	Visit	1 Scr ^b	24-Week Treatment Period (Part 1)												52-Week Additional Treatment Period (Part 2 - Optional) ^a		8-Week Observation Period (Optional)			
			2 BL	3	4	5	6	7	8	9	10 14 18 22	11 15 19 23	12 16 20 24	13 17 21 25	Additional Visits numbered sequentially	26 PEOT	27	28	29 FV	
	Week	-5 to -2	1	2	3	4	5	6	7	8	9	10 13 17 21	11 14 18 22	12 15 19 23	13 16 20 24	Every 4 weeks	Weekly in between site visits	25 or 77	27 or 79	29 or 81
Assessments	Visit type ^c	S	S	S	S	S	S	H ^d	S	H ^d	S	H ^d	H ^d	H ^d	S	H ^d	H ^d	S	H ^d	S

ADA=antidrug antibody; AE=adverse event; BL=baseline; CIDP=chronic inflammatory demyelinating polyradiculoneuropathy; C-SSRS=Columbia Suicide Severity Rating Scale; ECG=electrocardiogram; FV=Final Visit; H=Home visit; HIV=human immunodeficiency virus; ICF=Informed Consent form; IgA=immunoglobulin A; IgE=immunoglobulin E; IgG=immunoglobulin G; IgM=immunoglobulin M; IGRA=interferon gamma release assay; IMP=investigational medicinal product; INCAT=Inflammatory Neuropathy Cause and Treatment; iRODS=inflammatory Rasch-built Overall Disability Scale; IRT=interactive response technology; NF-L=neurofilament light chain; PEOT=premature end of treatment; PGIC=Patient Global Impressions of Change; PGIS=Patient Global Impressions of Severity; PK=pharmacokinetic; PRO=patient-reported outcome; RT-MRC=Rasch-built, modified-interval Medical Research Council scale, S=on-site visit; Scr=Screening visit; V=visit

Note: All assessments are to be completed in the order specified in the protocol or laboratory manual if possible. The ICF should be completed before any assessment. The PROs should be conducted in the order specified in Section 10.4 immediately after ICF (where applicable). The laboratory manual will provide further guidance on the order of sample collection.

^a The 52-week duration can be shortened or extended in view of the availability of an access program.

^{aa} Assessment to be performed before all other assessments at each visit except ICF.

^b Only for study participants with a gap period between the parent study and entry in CIDP04.

^c All visits have a ± 2 -day window. Minimum time between doses must be at least 5 days.

^d The following visits can be performed by a healthcare professional visiting the study participant at his/her home: Visits 11 to 13, 15 to 17, 19 to 21, and 23 to 25 (Weeks 10 to 12, 14 to 16, 18 to 20, and 22 to 24). Visits in Treatment Period Part 2 will follow the same pattern: one site visit followed by 3 visits

conducted at the participant home. Alternately, the visits can be conducted at the site as deemed necessary by site and/or study participant. Feasibility of IMP dosing in a home setting will have to be confirmed before the visit is conducted (see Section 8.2).

^e Will not be repeated at Visit 2 if performed at Visit 1.

^f If entry in CIDP04 (Visit 2) is done on the same day as the last visit of the parent study and in case assessment was performed at last visit of the parent study, data from the parent study will be used and corresponding assessments will not be repeated in CIDP04.

^g During site Visits 2, 3, and 4, vital signs will be measured prior to IMP administration, at the end of the infusion, and 2 and 4h after the end of the infusion. From Visit 5 until Visit 25, vital signs will be measured predose, at the end of the infusion and 2h after the end of the infusion only. During Treatment Period Part 2, vital signs will be measured predose, at the end of the infusion. At nondosing visits, vital signs need only be taken once during the visit. For study participants requiring additional assessments due to AEs (see Table 5-2), additional vital sign measurements may be taken based on the timing of the assessments.

^h Body weight is collected every 6 months during Treatment Period Part 2 starting at first visit in this period and will be used to select the correct volume for dose infusion from these timepoints.

ⁱ A full C-SSRS assessment will be performed only when the study participant has a positive response to the suicidal ideation query. If a study participant has active suicidal ideation as confirmed by the answer “Yes” to Question 4 or Question 5 of the C-SSRS assessments, the study participant will be excluded or withdrawn from the study and immediately referred to a Mental Healthcare Professional.

^j Only performed every 24 weeks.

^k Not required for study participants who had a Screening Visit.

^l The full neurological examination includes a fundoscopy. In addition to the FV, a full neurological examination should be performed for any study participant who experiences severe headache (refer to Section 5.2.1 and Table 5-2).

^m Assessment to be performed every 12 weeks (Weeks 25, 37, 49 and 61).

ⁿ Serology includes hepatitis C virus (HCV)-antibodies (Ab)+, hepatitis B virus antibodies (HBsAg and HBcAb), human immunodeficiency virus antibodies (HIV1 and HIV2).

^o In case of immediate entry from the parent study, the serum pregnancy test from the parent study should not be older than 5 weeks prior to entry into this CIDP04 study and the urine pregnancy test done at Visit 2 must both be negative before dosing. In case of gap period between the parent study and entry in CIDP04, a serum test will be performed at Visit 1 (Screening). Pregnancy testing will consist of urine testing at dosing visits during the Treatment Period Part 1, monthly urine testing during Treatment Period Part 2 and at each visit during the Observation Period for women of childbearing potential. A positive urine pregnancy test must be confirmed using a serum pregnancy test. Note that the final urine pregnancy test of the study should be no longer than 90 days after the final dose of IMP.

^p The IGRA test will be performed in a central laboratory.

^q Tuberculosis signs and symptoms Questionnaire must be done at least every 12 weeks.

^r Self-administration may be performed by study participant under the supervision of the home nurse after full training.

^s Trough PK samples should be taken for all study participants receiving rozanolixizumab. At Visits 2, 4, and 8, PK samples should be taken predose and 4h postdose for all study participants. At Visits 14, 18, 22 and quarterly at site visits during Treatment Period Part 2, a predose sample only should be taken. At Visit 26, samples to be taken once during the visit.

^t Does not apply to Visit 10.

^u Serum complement (C3, C4), plasma complement (C3a, C5a), and serum cytokines should be taken predose at Visit 2 for all study participants. Samples should be taken predose and 4h postdose for all study participants at other scheduled visits (Visits 3, 8, 10, 14, 18, 22 and at first (Week 25) and last visit (Week 73) of Treatment Period Part 2); if an infusion reaction occurs within the first 2h, refer to Section 5.2.1 and Table 5-2.

^v Only at Visit 14.

^w In case IgG levels are below 2 and the study participant does not qualify for a withdrawal, IgG levels will be monitored weekly.

^x Assessments to be performed only at the first visit after Visit 25 (ie, 1st visit of Part 2). Visit 29/FV should not be performed after Treatment Period 2.

^y Only performed at PEOT visit when starting Observation Period directly after Treatment Period Part 1

^z At Visits 2, 3, 8, 10, 14, 18, and 22, samples for exploratory biomarkers should be taken predose. See [Table 5-2](#) for sampling in case of AE of interest.

This document cannot be used to support any marketing authorization application and any extensions or variations thereof
PUBLIC COPY

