6.2 Exclusion criteria

Study participants are not permitted to enroll in the study if any of the following criteria is met:

1. Study participant is currently participating in another study of an IMP (or a medical device).
2. Female study participant who is pregnant or lactating, or planning to become pregnant during the study and until 2 months following completion of the study.
3. Study participant has any medical (acute or chronic illness) or psychiatric condition that, in the opinion of the investigator, could harm the study participant or would compromise the study participant's ability to participate in this study.
4. Study participant has 12-lead ECG with abnormalities considered to be clinically significant upon medical review.
5. Study participant has renal impairment, defined as serum creatinine level of ≥ 1.4 mg/dL for females and ≥ 1.5 mg/dL for males.
6. Study participant has an absolute neutrophil count $< 1500/\text{mm}^3$ ($1.5 \times 10^9/\text{L}$).
7. Study participant has > 2 x upper limit of normal (ULN) of any of the following: alanine aminotransferase (ALT), aspartate aminotransferase (AST), or alkaline phosphatase (ALP), or $>$ ULN total bilirubin ($\ge 1.5 \times \text{ULN}$ total bilirubin if known Gilbert's syndrome). If study participant has elevations only in total bilirubin that are $>$ ULN and $< 1.5 \times \text{ULN}$, fractionate bilirubin to identify possible undiagnosed Gilbert's syndrome (ie, direct bilirubin $< 35\%$).

For study participants with a Baseline result $>$ ULN for ALT, AST, ALP, or total bilirubin, a Baseline diagnosis and/or the cause of any clinically meaningful elevation must be understood and recorded in the electronic Case Report form (eCRF).

If study participant has $>$ ULN ALT, AST, or ALP that does not meet the exclusion limit at the time of entry in CIDP04 (either Screening [Visit 1] or Baseline [Visit 2]), repeat the tests, if possible, prior to dosing to ensure there is no further ongoing clinically relevant increase. In case of a clinically relevant increase, inclusion of the study participant must be discussed with the Medical Monitor.

Tests that result in ALT, AST, or ALP up to 25% above the exclusion limit may be repeated once for confirmation. This applies to study participants who had a Screening Visit and includes rescreening.

8. Study participant has a clinically relevant active infection (eg, sepsis, pneumonia, abscess).

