This document cannot be used to support any market authorization application and any extension of marketing authorization

Table 6-1: Time restrictions required prior to Baseline Visit (Visit 2) for immunosuppressants, biologics, and other therapies

Generic name	Time restrictions required prior to Baseline Visit (regardless of route)
Immunosuppressants	
Cyclophosphamide	
Pimecrolimus	
Vinca alkaloids (vincristine, vinblastine)	
Biologics (mAbs and fusion proteins)	
Abatacept (CTLA 4-Ig)	
Belimumab	
Golimumab	
Natalizumab	
Ofatumumab	
Rituximab	
Ocrelizumab	
Atacicept (TACI-Ig)	
Veltuzumab	
Other biologics	
Others	
Rigerimod	
PLEX	

CTLA 4-Ig=cytotoxic T lymphocyte-associated molecule-4 immunoglobulin; mAb=monoclonal antibody;
PLEX=plasma exchange; TACI-Ig=transmembrane activator and calcium modulator and cyclophilin ligand interactor-immunoglobulin

NOTE: For other immunotherapies not included in the table, consult with Medical Monitor prior to enrollment.

6.3 Rescreening of study participants (only for study participants who had a Screening Visit)

For study participants otherwise fully eligible but not able to enter the study as planned for nonclinical reasons, rescreening may be allowed at the discretion of the investigator, following discussion with the sponsor's Medical Monitor and/or Study Physician.

If a study participant has 1 isolated test result in the exclusionary range that is deemed not being clinically significant by the investigator, retesting may be allowed at the discretion of the investigator, following discussion with the sponsor's Medical Monitor and/or Study Physician. If the normalization of the test result occurs within the Screening Period, then no other screening procedures need to be repeated.

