8.1 Screening, Visit 1 (Weeks -5 to -2)

The Screening Visit is only for study participants with a gap period between the parent study and entry in CIDP04.

The following procedures will be performed at the Screening Visit (or as close as possible to the Screening date):

- Informed consent process including obtaining written informed consent from the study participant
- iRODS assessment
- Query for suicidality (C-SSRS)
- Tuberculosis Signs and Symptoms Questionnaire
- Record study participant demographics
- Verify (to the extent possible with available information at Screening, Visit 1) that study participant fulfills all the inclusion criteria and none of the exclusion criteria
- Medical history update
- Prior and concomitant medications
- Concomitant medical procedures
- Vital signs (taken once during the visit)
- Body weight (Screening weight will be used for calculation of the infusion dose)
- Recording of AEs
- 12-lead ECG
- Full physical examination
- Full neurological examination
- Contact IRT
- Blood sample (the Laboratory Manual will provide guidance on the order of sample collection) for:
 - Clinical laboratory tests (ie, hematology, clinical chemistry, serology [including hepatitis C and hepatitis B virus-antibodies, HIV1, and HIV2], and interferon gamma release assay [IGRA] for active and latent TB)
 - Serum pregnancy test for women of childbearing potential
 - Immunoglobulins (total IgG and IgG subclasses)
 - Vaccination-specific antibody titers (tetanus and influenza Type A)
- Urine sample for urinalysis
- INCAT assessment

- Assessment of grip strength by site personnel
- RT-MRC assessment
- Provide an appointment to the next visit according to the following guidance:
 - For study participants on an IVIg 3- to 6-week regimen, Baseline Visit should occur 1 week before the next planned IVIg dose (according to the Baseline IVIg regimen). However, if that specific date is not possible, the Baseline Visit (Visit 2) could be up to 1 week after that date.
 - Study participants on a 2-week IVIg treatment regimen will continue on their regular schedule for 1 further IVIg treatment until Visit 2. Visit 2 will occur 1 week before the planned IVIg dose. However, if that specific date is not possible, Visit 2 could be up to 1 week after that date.

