8.2.1 Visit 2, Baseline (Week 1)

The following procedures will be performed at Visit 2 (Week 1). If study participant enters CIDP04 at Visit 2 and the assessment was performed at the last visit in the parent study (eg, CIDP01) (or at Visit 16 for NF-L), the assessment will not be repeated and will be marked as "not to repeat" in the list below:

- Informed consent process including obtaining written informed consent from the study participant (for study participants who did not perform Screening Visit [Visit 1])
- PROs should be conducted in the order specified in Section 10.4:
 - iRODS assessment - to be performed before any other assessment (not to repeat)
 - CIDP PRO instrument (not to repeat)
 - Fatigue scale (not to repeat)
 - PGIS (not to repeat)
 - PGIC (not to repeat) - not required for study participants who had a Screening Visit
- Query for suicidality (not to repeat)
- Record study participant demographics (for study participants who did not perform Screening Visit [Visit 1])
- Verify that study participant fulfills all the inclusion criteria and none of the exclusion criteria (for study participants who did not perform Screening Visit [Visit 1])
- Withdrawal criteria assessment
- Medical history update (for study participants who did not perform Screening Visit [Visit 1])
- Prior and concomitant medications (not to repeat)
- Concomitant medical procedures (not to repeat)
- Vital signs (prior to IMP administration, at the end of the infusion, at 2 and 4h after the end of the infusion)
- Body weight assessment (Visit 2 weight will be used for calculation of the infusion dose for study participants without screening visit) (not to repeat)
- Recording of AEs (not to repeat)
- Full physical examination (not to repeat)
- Full neurological examination (not to repeat)

- 12-lead ECG (not to repeat)
- Blood sample (all samples should be taken predose unless otherwise specified; the Laboratory Manual will provide guidance on the order of sample collection) for:
 - Clinical laboratory tests (ie, hematology, clinical chemistry, and IGRA for active and latent TB) (not to repeat)
 - PK of rozanolixizumab (predose and 4h postdose) (not to repeat predose sample if performed at last visit in the parent study)
 - ADA (anti-rozanolixizumab antibodies) (not to repeat)
 - Serum complement (C3, C4) and plasma complement (C3a, C5a)
 - Serum cytokines (predose)
 - Immunoglobulins (total IgG and IgG subclasses) (not to repeat)
 - IgA, IgM, IgE (not to repeat)

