15 ETHICS AND REGULATORY REQUIREMENTS

15.1 Informed consent

Study participant's informed consent must be obtained and documented in accordance with local regulations, ICH-GCP requirements, and the ethical principles that have their origin in the principles of the Declaration of Helsinki.

Prior to obtaining informed consent, information should be given in a language and at a level of complexity understandable to the study participant in both oral and written form by the investigator (or designee). Each study participant will have the opportunity to discuss the study and its alternatives with the investigator.

Prior to participation in the study, the ICF should be signed and personally dated by the study participant, or his/her legal representative, and by the person who conducted the informed consent discussion (investigator or designee). The study participant or his/her legal representative must receive a copy of the signed and dated ICF. As part of the consent process, each study participant must consent to direct access to his/her medical records for study-related monitoring, auditing, IRB/IEC review, and regulatory inspection.

If the ICF is amended during the study, the investigator (or the sponsor, if applicable) must follow all applicable regulatory requirements pertaining to the approval of the amended ICF by the IRB/IEC and use of the amended form.

All studies conducted at centers in the United States must include the use of a Health Insurance Portability and Accountability Act Authorization form.

The study participant may withdraw his/her consent to participate in the study at any time. A study participant is considered as enrolled in the study when he/she has signed the ICF. An eCRF must not be started, nor may any study specific procedure be performed for a given study participant, without having obtained his/her written consent to participate in the study.

Any data already generated on the samples will be retained and used, but no further laboratory analysis will occur.

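### Gap entrants have no scheduled, documented eligibility check after Visit 1, so new events in the 14 to 35 days before first dose are not tested against exclusions 22 and 24 to 27

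*Protocol*

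**What the plan says.** Protocol Section 5.1 gives gap entrants a Screening Period of 2 to 5 weeks, partly "to confirm that the study participant still meets the eligibility criteria for entry in the OLE study". Table 5-1 footnote b restricts Visit 1 to this group.

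Table 5-1 marks verification of inclusion and exclusion criteria at Visits 1 and 2, under footnote e: "Will not be repeated at Visit 2 if performed at Visit 1". Section 8.2.1 agrees. At Visit 2 the investigator verifies that the participant meets all inclusion and "none of the exclusion criteria (for study participants who did not perform Screening Visit [Visit 1"]). The medical history item has the same restriction: "Medical history update (for study participants who did not perform Screening Visit [Visit 1"]).

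Section 8.1 words the Visit 1 check as provisional: "Verify (to the extent possible with available information at Screening, Visit 1").

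Section 6.2.1 adds exclusions 14 to 27 for gap entrants only. Five of them have look-backs that end at first dose (22) or at Baseline (24, 25 and 26, and 27 through Table 6-1).

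**The concern.** The Visit 2 verification is kept for direct rollovers, to whom exclusions 14 to 27 do not apply, and cancelled for gap entrants, to whom they do. No participant is therefore scheduled to have exclusions 22 and 24 to 27 verified at the time those criteria refer to. Gap entrants have also been outside the parent study on other treatment, so interval events are more plausible for them than for same-day entrants.

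History known at Visit 1 can be projected forward, because the Visit 2 appointment is set at that visit. New events after Visit 1 cannot. If one is missed, a participant who meets an exclusion could receive an IgG-lowering drug and be recognised only afterwards as an eligibility deviation. Anyone dosed enters the Safety Set (Protocol 14.1.2, SAP 3.5.2), so the case would also count in the primary safety summary.

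**Working it through.** **Interval between the only scheduled check and first dose.** The Screening Period in Protocol 5.1 is 2 to 5 weeks: 2 × 7 = 14 days and 5 × 7 = 35 days. As a cross-check, the periods in SAP 3.2.1.2 add up to the stated maximum duration: 5 + 24 + 52 + 8 = 89 weeks. If the ±2-day visit window (footnote c) applies to this interval, it becomes 14 − 2 = 12 to 35 + 2 = 37 days.

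**Criteria whose look-back ends after Visit 1 (Section 6.2.1).**
- 22: serious infection (hospitalization or parenteral antibiotics) in the 4 weeks before first dose.
- 24: live vaccine in the 8 weeks before Baseline.
- 25: experimental biological agent in the 3 months or 5 half-lives before Baseline, whichever is longer.
- 26: rituximab, ofatumumab or ocrelizumab in the 6 months before Baseline, or 12 months if B cells are not in the normal range.
- 27: therapies in Table 6-1, with windows before Baseline. The durations are blacked out in this copy.

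**What the plan provides, and what each item tests.**
- *Exclusion 11* bars anyone intending a live vaccination during the study. Section 9.1.1.1 treats the study as running from consent, so a vaccine planned for the Screening Period is already barred at Visit 1. An unplanned one is not.
- *Exclusion 1* bars current participation in another IMP study, which narrows criterion 25. Use outside a study stays open.
- *Withdrawal-criteria assessment*, scheduled at Visit 2 for all: Section 6.4 names an interfering illness and PLEX, dexamethasone or rituximab. It names neither live vaccines nor the other Table 6-1 therapies.
- *AE and concomitant-medication recording* at Visit 2, with AEs collected from consent and SAEs reportable within 24 hours: this would probably capture the relevant fact, and a hospitalized infection would already have been reported. No listed step compares these records with the look-backs.
- *Physical and neurological examination, ECG, vital signs and laboratory tests* at Visit 2: these bear on an infection still active, not one that has resolved.
- *Section 6.4.1.1* stops treatment for a serious infective episode, including one needing iv antibiotics. It contains no look-back before the first dose.
- *Section 7.8.2* prohibits a list of therapies during the Treatment Period. A therapy continuing at Visit 2 meets that rule; a course completed during Screening does not. Vinca alkaloids are in Table 6-1 but not in the 7.8.2 list.

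Three items have their own predose gate and lie outside this point: suicidality (exclusion 9), the urine pregnancy test (inclusion 4) and IGRA (Section 9.3.6).

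**Remainder.** An unplanned live vaccine, a resolved infection treated with parenteral antibiotics, or a completed course of an excluded therapy, in each case between Visit 1 and Visit 2. With a predose verification at Visit 2, the unchecked interval falls from 14 to 35 days to 0 days.

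**The case against.** The strongest reply is that the requirement is intact and only a checklist entry is missing. Section 7.2 gives rozanolixizumab to eligible participants, Section 5.1 makes confirming eligibility a purpose of the whole Screening Period, and criteria worded to first dose or Baseline bind the investigator on that day. Visit 2 collects the medication and AE data that would reveal a problem, alongside the safeguards above. All of this stands, and it keeps the point minor. It does not remove the point, because two concordant places in the protocol tell the site not to repeat the verification. A site that follows them has no documented predose confirmation.

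A reader might infer that the protocol permits dosing of someone who became ineligible after Visit 1. Section 6.2 says "Study participants are not permitted to enroll in the study if any of the following criteria is met", and Section 15.1 adds that "A study participant is considered as enrolled in the study when he/she has signed the ICF", which for gap entrants is at Visit 1. That reading is too literal, since Section 7.2 ties dosing to eligibility.

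A reader might also infer that exclusions depending on Visit 1 samples (5, 6, 7, 14, 19) go unconfirmed. The documents do not support that either. Exclusion 7 asks for certain raised liver tests to be repeated before dosing if possible, and the rescreening rule in 6.3 presupposes that results are compared with the limits: "If the normalization of the test result occurs within the Screening Period, then no other screening procedures need to be repeated". What is absent there too is a scheduled, documented final step.

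**Conclusion.** The point holds as a minor, procedural gap confined to gap entrants. A stated rule cancels the eligibility check at the time to which exclusions 22 and 24 to 27 refer, and no other scheduled item makes that comparison before dosing. The unchecked interval is nominally 14 to 35 days and is the same for every one of these criteria.

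It is tempting to express the interval as a share of each look-back, for example 14/28 = 50% at the shortest Screening Period for criterion 22. That would only rank the criteria by the length of their windows; it measures neither exposure nor the chance of a breach. The documents give neither the number of gap entrants nor the frequency of such events, so no expected number of misses can be derived. The analysis plan itself is unaffected.

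The conclusion rests on reading Table 5-1 and Sections 8.1 and 8.2.1 as the full list of scheduled steps. A site worksheet or manual outside these documents could already contain the check.

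**What to change.** Two wording changes to the protocol:
1. In Table 5-1, remove footnote e from the row for verification of inclusion and exclusion criteria, and leave it on the other rows.
2. In Section 8.2.1, replace the parenthesis that limits this item to participants without a Screening Visit with the word predose.

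Eligibility is then confirmed before the first dose for everyone. For gap entrants the confirmation should cover interval history since Visit 1 and the Screening laboratory results, so the medical history row need not change.

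The cost is a few minutes at Visit 2 and an occasional late screen failure. A late failure need not cost an Ig dose. Section 8.1 places Visit 2 one week before the next planned IVIg dose, with up to one week's delay allowed, or on the planned SC Ig dose day within 2 days.
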